11.44 Overall Objective Status

The overall objective status for an evaluation is determined by combining the patient's status on target lesions, target lymph nodes, non-target lesions, non-target lymph nodes, and new disease as defined in the following table:

Target Lesions and Target Lymph Nodes	Non-Target Lesions and Non-Target Lymph Nodes	New Sites of Disease	Overall Objective Status
CR	CR	No	CR
CR	Non-CR/Non-PD	No	PR
PR	CR		
PR	Non-CR/Non-PD	No	PR
CR/PR	Not All Evaluated*	No	PR
SD	CR Non-CR/Non-PD Not All Evaluated*	No	SD
Not all Evaluated	CR Non-CR/Non-PD Not All Evaluated*	No	Not Evaluated (NE)
PD	Uequivocal PD CR Non-CR/Non-PD Not All Evaluated*	Yes or No	PD
CR/PR/SD/PD/Not all Evaluated	Uequivocal PD	Yes or No	PD
CR/PR/SD/PD/Not all Evaluated	CR Non-CR/Non-PD Not All Evaluated*	Yes	PD

*See Section 11.431

11.45 Symptomatic Deterioration: Patients with global deterioration of health status requiring discontinuation of treatment without objective evidence of disease progression at that time, and not either related to study treatment or other medical conditions, should be reported as PD due to “symptomatic deterioration.” Every effort should be made to document the objective progression even after discontinuation of treatment due to symptomatic deterioration. A patient is classified as having PD due to “symptomatic deterioration” if any of the following occur that are not either related to study treatment or other medical conditions:

- Weight loss >10% of body weight.
- Worsening of tumor-related symptoms.
- Decline in performance status of >1 level on ECOG scale.

11.5 Antitumor Effect – Immune Response Criteria

Wolchok et al [34] described the Immune Response Criteria (IRC) which was used to evaluate response to nivolumab and ipilimumab in melanoma. The IRC is derived from the WHO criteria and is characterized by the following features:

- Objective response is based on the total measurable tumor burden: For the irRC, only index and measurable new lesions are taken into account.
- At the baseline tumor assessment, the sum of the products of the two largest perpendicular diameters (SPD) of all index lesions (five lesions per organ, up to 10 visceral lesions and five cutaneous index lesions) is calculated. At each subsequent tumor assessment, the SPD of the index lesions and of new, measurable lesions ($\geq 5 \times 5$ mm; up to 5 new lesions per organ: 5 new cutaneous lesions and 10 visceral lesions) are added together to provide the total tumor burden:

$$\text{Tumor Burden} = \text{SPD}_{\text{index lesions}} + \text{SPD}_{\text{new, measurable lesions}}$$

- Complete response: Disappearance of all lesions in two consecutive observations not less than 4 weeks apart.
- Partial response: $\geq 50\%$ decrease in tumor burden compared with baseline in two observations at least 4 weeks apart (within 8 weeks and not less than 4 weeks apart).
- Stable disease: 50% decrease in tumor burden compared with baseline cannot be established nor 25% increase compared with nadir.
- Progressive disease: At least 25% increase in tumor burden compared with nadir (at any single time point) in two consecutive observations at least 4 weeks apart.
- At each tumor assessment, the response in index and new, measurable lesions is defined based on the change in tumor burden (after ruling out PD). Decreases in tumor burden must be assessed relative to baseline measurements (i.e., the SPD of all index lesions at screening).

Measurable lesions	Non-measurable Lesions		Overall Response
Index and new, measurable lesions (tumor burden),* %	Non-index lesions	New, non-measurable lesions	
↓100	Absent	Absent	CR†
↓100	Stable	Any	PR†
↓100	Unequivocal progression	Any	PR†
↓≥50	Absent/ Stable	Any	PR†
↓≥50	Unequivocal progression	Any	PR†
↓<50 to <25↑	Absent/ Stable	Any	SD
↓<50 to <25↑	Unequivocal progression	Any	SD
≥ 25 ?	Any	Any	PD

*Decreases assessed relative to baseline, including measurable lesions only (> 5 × 5 mm).

†Assuming response (CR) and progression (PD) are confirmed by a second, consecutive assessment at least 8 weeks apart in this protocol.

12. DATA REPORTING / REGULATORY REQUIREMENTS

Adverse event lists, guidelines, and instructions for AE reporting can be found in Section 7.0 (Adverse Events: List and Reporting Requirements).

12.1 Data Reporting

Data collection for this study will be done exclusively through Medidata Rave. Access to the trial in Rave is granted through the iMedidata application to all persons with the appropriate roles assigned in the Regulatory Support System (RSS). To access Rave via iMedidata, the site user must have an active CTEP IAM account (<https://eapps-ctep.nci.nih.gov/iam>) and the appropriate Rave role (Rave CRA, Read-Only, or Site Investigator) on either the Corresponding Organization or Participating Organization roster at the enrolling site.

Upon initial site registration approval for the study in RSS, all persons with Rave roles assigned on the appropriate roster will be sent a study invitation e-mail from iMedidata. To accept the invitation, site users must log into the Select Login (<https://login.imedidata.com/selectlogin>) using their CTEP-IAM user name and password, and click on the “accept” link in the upper right-corner of the iMedidata page. Please note, site users will not be able to access the study in Rave until all required Medidata and study specific trainings are completed. Trainings will be in the form of electronic learnings (eLearnings), and can be accessed by clicking on the link in the upper right pane of the iMedidata screen.

Users that have not previously activated their iMedidata/Rave account at the time of initial

site registration approval for the study in RSS will also receive a separate invitation from iMedidata to activate their account. Account activation instructions are located on the CTSU website, Rave tab under the Rave resource materials (Medidata Account Activation and Study Invitation Acceptance). Additional information on iMedidata/Rave is available on the CTSU members' website under the Rave tab or by contacting the CTSU Help Desk at [name] or by e-mail at [contact].

12.1.1 Method

This study will be monitored by the Clinical Trials Monitoring Service (CTMS). Data will be submitted to CTMS at least once every two weeks via Medidata Rave (or other modality if approved by CTEP). Information on CTMS reporting is available at: <http://www.theradex.com/CTMS>. On-site audits will be conducted on an 18-36 month basis as part of routine cancer center site visits for U.S. and Canadian sites. CTRG sites will be audited under the previously established procedures for Mayo P2C CTRG participation. More frequent audits may be conducted if warranted by accrual or due to concerns regarding data quality or timely submission. For CTMS monitored studies, after users have activated their accounts, please contact the Theradex Help Desk at [contact] or by email at [contact] for additional support with Rave and completion of CRFs.

12.1.2 Responsibility for Data Submission

For ETCTN trials, it is the responsibility of the PI(s) at the site to ensure that all investigators at the ETCTN Sites understand the procedures for data submission for each ETCTN protocol and that protocol specified data are submitted accurately and in a timely manner to the CTMS via the electronic data capture system, Medidata Rave.

Data are to be submitted via Medidata Rave to CTMS on a real-time basis, but no less than once every 2 weeks. The timeliness of data submissions and timeliness in resolving data queries will be tracked by CTMS. Metrics for timeliness will be followed and assessed on a quarterly basis. For the purpose of Institutional Performance Monitoring, data will be considered delinquent if it is greater than 4 weeks past due.

Data from Medidata Rave and CTEP-AERS is reviewed by the CTMS on an ongoing basis as data is received. Queries will be issued by CTMS directly within Rave. The queries will appear on the Task Summary Tab within Rave for the CRA at the ETCTN to resolve. Monthly web-based reports are posted for review by the Drug Monitors in the IDB, CTEP. Onsite audits will be conducted by the CTMS to ensure compliance with regulatory requirements, GCP, and NCI policies and procedures with the overarching goal of ensuring the integrity of data generated from NCI-sponsored clinical trials, as described in the ETCTN Program Guidelines, which may be found on the CTEP (http://ctep.cancer.gov/protocolDevelopment/electronic_applications/adverse_events.htm) and CTSU websites.

An End of Study CRF is to be completed by the PI, and is to include the recommended phase 2 dose (RP2D), and a description of any dose-limiting toxicities (DLTs). CTMS will utilize

a core set of eCRFs that are Cancer Data Standards Registry and Repository (caDSR) compliant (<http://cbiit.nci.nih.gov/ncip/biomedical-informatics-resources/interoperability-and-semantics/metadata-and-models>). Customized eCRFs will be included when appropriate to meet unique study requirements. The PI is encouraged to review the eCRFs, working closely with CTMS to ensure prospectively that all required items are appropriately captured in the eCRFs prior to study activation. CTMS will prepare the eCRFs with built-in edit checks to the extent possible to promote data integrity.

CDUS data submissions for ETCTN trials activated after March 1, 2014, will be carried out by the CTMS contractor, Theradex. CDUS submissions are performed by Theradex on a monthly basis. The trial's lead institution is responsible for timely submission to CTMS via Rave, as above.

Further information on data submission procedures can be found in the ETCTN Program Guidelines
(http://ctep.cancer.gov/protocolDevelopment/electronic_applications/adverse_events.htm).

See Section 12.1.1 for details on CDUS reporting. As the data management center for this trial, Theradex is responsible for compiling and submitting CDUS data to CTEP for all participants and for providing the data to the Principal Investigator for review.

12.2 Collaborative Agreements Language

The agent(s) supplied by CTEP, DCTD, NCI used in this protocol is/are provided to the NCI under a Collaborative Agreement (CRADA, CTA, CSA) between the Pharmaceutical Company(ies) (hereinafter referred to as "Collaborator(s)") and the NCI Division of Cancer Treatment and Diagnosis. Therefore, the following obligations/guidelines, in addition to the provisions in the "Intellectual Property Option to Collaborator"
(http://ctep.cancer.gov/industryCollaborations2/intellectual_property.htm) contained within the terms of award, apply to the use of the Agent(s) in this study:

1. Agent(s) may not be used for any purpose outside the scope of this protocol, nor can Agent(s) be transferred or licensed to any party not participating in the clinical study. Collaborator(s) data for Agent(s) are confidential and proprietary to Collaborator(s) and shall be maintained as such by the investigators. The protocol documents for studies utilizing Agents contain confidential information and should not be shared or distributed without the permission of the NCI. If a copy of this protocol is requested by a patient or patient's family member participating on the study, the individual should sign a confidentiality agreement. A suitable model agreement can be downloaded from: <http://ctep.cancer.gov>.
2. For a clinical protocol where there is an investigational Agent used in combination with (an)other Agent(s), each the subject of different Collaborative Agreements, the access to and use of data by each Collaborator shall be as follows (data pertaining to such combination use shall hereinafter be referred to as "Multi-Party Data"):

- a. NCI will provide all Collaborators with prior written notice regarding the existence and nature of any agreements governing their collaboration with NCI, the design of the proposed combination protocol, and the existence of any obligations that would tend to restrict NCI's participation in the proposed combination protocol.
 - b. Each Collaborator shall agree to permit use of the Multi-Party Data from the clinical trial by any other Collaborator solely to the extent necessary to allow said other Collaborator to develop, obtain regulatory approval or commercialize its own Agent.
 - c. Any Collaborator having the right to use the Multi-Party Data from these trials must agree in writing prior to the commencement of the trials that it will use the Multi-Party Data solely for development, regulatory approval, and commercialization of its own Agent.
3. Clinical Trial Data and Results and Raw Data developed under a Collaborative Agreement will be made available to Collaborator(s), the NCI, and the FDA, as appropriate and unless additional disclosure is required by law or court order as described in the IP Option to Collaborator (http://ctep.cancer.gov/industryCollaborations2/intellectual_property.htm). Additionally, all Clinical Data and Results and Raw Data will be collected, used and disclosed consistent with all applicable federal statutes and regulations for the protection of human subjects, including, if applicable, the Standards for Privacy of Individually Identifiable Health Information set forth in 45 C.F.R. Part 164.
4. When a Collaborator wishes to initiate a data request, the request should first be sent to the NCI, who will then notify the appropriate investigators (Group Chair for Cooperative Group studies, or PI for other studies) of Collaborator's wish to contact them.
5. Any data provided to Collaborator(s) for Phase 3 studies must be in accordance with the guidelines and policies of the responsible Data Monitoring Committee (DMC), if there is a DMC for this clinical trial.
6. Any manuscripts reporting the results of this clinical trial must be provided to CTEP by the Group office for Cooperative Group studies or by the principal investigator for non-Cooperative Group studies for immediate delivery to Collaborator(s) for advisory review and comment prior to submission for publication. Collaborator(s) will have 30 days from the date of receipt for review. Collaborator shall have the right to request that publication be delayed for up to an additional 30 days in order to ensure that Collaborator's confidential and proprietary data, in addition to Collaborator(s)'s intellectual property rights, are protected. Copies of abstracts must be provided to CTEP for forwarding to Collaborator(s) for courtesy review as soon as possible and preferably at least three (3) days prior to submission, but in any case, prior to presentation at the meeting or publication in the proceedings. Press releases and other

media presentations must also be forwarded to CTEP prior to release. Copies of any manuscript, abstract and/or press release/ media presentation should be sent to:

Email: [contact]

The Regulatory Affairs Branch will then distribute them to Collaborator(s). No publication, manuscript or other form of public disclosure shall contain any of Collaborator's confidential/ proprietary information.

13. STATISTICAL CONSIDERATIONS

13.1 Study Design/Endpoints

13.1.1 Background/Overview

In a study of nivolumab alone, the response rates were 18% in lung cancer, 28% in melanoma and 27% in renal-cell cancer (RCC). Over 60% of responders have durable responses lasting > 1 year [23], the PFS at 24 weeks was 41% for melanoma, 26% for lung cancer and 56% for RCC. In the phase 1 study, the median duration of therapy was 12 weeks (range, 2 to 111), and the objective response rates were: 17% in melanoma, 11% in RCC, 10% in lung cancer and 5% in ovarian cancer. Responses > 1 year were reported in 50% of patients [35]. In general, there is a paucity of data on PFS at 24 weeks, SD rate and other survival data from studies involving multiply-treated NPC patients. Data from phase II 2nd line studies of cytotoxic agents such as a gemcitabine and capecitabine, reported the SD rate to be around 30-49%, median TTP of 3.6-5 months, and *PFS at 6 months of around 30-40% (*estimated from the published curves) [36-38]. The overall response rate (ORR) for cytotoxic agents in patients who failed only 1 prior line of chemotherapy is estimated to be around 20%, but the response is usually not durable [36-38]. The problem of using such data for this proposal is that nearly all patients from these studies had just 1 prior line of therapy, while the current proposal (and also published studies on nivolumab) enrolled patients who were more heavily pre-treated.

Therefore, we have decided to use the data from two of our prior phase II studies of targeted agents, namely, pazopanib and cetuximab (the latter in combination with carboplatin) for calculating the sample size in this proposal because the cohort in these studies are similar to the current proposal. In the pazopanib study, patients had a median of 3 lines of therapy, and clinical benefit rate (CBR, PR + SD + CR) at 12 weeks was used to calculate the sample size. A CBR of 35% was estimated to be clinically meaningful, and the actual rate reported was > 50% [39]. The ORR was 6.1%, median TTP was 4.4 months (95% CI: 3.9–5.8 months) and the PFS-6 month was around 30-35% (read from the curve). In the cetuximab study [40], 70% of patients had 1 prior line of chemotherapy only. Although the ORR was 11.7% and the CBR rate was 60% (which is higher than the pazopanib study), the median TTP was quite short at 2.7 months, and the PFS-6 months was around 20-30% (read off the curve) [40]. Therefore, the average PFS at 24 weeks (6 months) is around 25-30% a benchmark for heavily-pretreated NPC patients, with a ORR between 6% to 20%.

These prior studies have shown that the response rate is generally around 5% in this disease setting [39-40]. If Nivolumab can increase the response rate to 20% or more, that would be exciting and worth further study. This protocol will assess the confirmed response rate as the primary endpoint. In addition this study will assess multiple secondary endpoints, including adverse events, tumor response to nivolumab based on immune-related response criteria (IRC), duration of response, progression-free survival (PFS), overall survival (OS), and laboratory correlates.

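### Section 13.1.5 misprints the rule's early-stopping and success probabilities at 5% (exact 73.6% and 0.080, not 64.5% and 0.09), and 13.1.1 credits that 5% to studies it reports at 6.1% and 11.7%

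*Combined protocol and SAP*

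**What the plan says.** Section 13.1.4 fixes the rule. At 20 evaluable patients, fewer than 2 confirmed responses stops the study and the treatment is considered ineffective; 2 or more lets it go on. At 35 evaluable patients, 4 or more confirmed responses is a positive result and 3 or fewer is negative.

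Section 13.1.5 gives four properties of this rule: 90% power at a true confirmed response rate of 20%, a significance level of 0.09 at 5%, and early-stopping probabilities of 64.5% at 5% and 7% at 20%.

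Section 13.1.1 explains the choice of rates. It sets aside second-line cytotoxic data because nearly all of those patients had one prior line, "while the current proposal (and also published studies on nivolumab) enrolled patients who were more heavily pre-treated". It turns instead to two earlier phase II studies, "namely, pazopanib and cetuximab (the latter in combination with carboplatin", chosen "because the cohort in these studies are similar to the current proposal". For the first it says "In the pazopanib study, patients had a median of 3 lines of therapy" and "The ORR was 6.1%, median TTP was 4.4 months". For the second it says "In the cetuximab study [40], 70% of patients had 1 prior line of chemotherapy only" and "Although the ORR was 11.7% and the CBR rate was 60" percent. It then summarises the benchmark ORR as 6% to 20%. The next paragraph reads "These prior studies have shown that the response rate is generally around 5% in this disease setting [39-40", and sections 13.1.3 and 13.1.5 use 5% as the null rate.

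**The concern.** There are two faults, and they are independent of each other.

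First, two of the four printed operating characteristics do not follow from the printed rule. Both are at 5%, the rate at which the design is meant to show that it protects against pursuing an inactive agent. A reader who checks 13.1.5 cannot tell whether the rule or the probabilities are mistaken.

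Second, the null rate is the only comparator in a single-arm trial, so its source matters. The source given is two studies. As the same section reports them, neither is as low as 5%, and the section's own range starts above 5%. No step from 6.1% and 11.7% to 5% is written down.

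**Working it through.** **Inputs.** From 13.1.4: n1 = 20, continue at 2 or more; n = 35, so 15 further patients; success at 4 or more. From 13.1.3 and 13.1.5: true rates p = 5% and 20%. From 13.1.1: reported ORRs of 6.1% and 11.7%.

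**Early stopping.** P(stop) = P(X ≤ 1), with X ~ Bin(20, p).
- p = 20%: 0.0115 + 0.0576 = 0.069. The printed 7% is reproduced.
- p = 5%: 0.3585 + 0.3774 = 0.736. The printed value is 64.5%, a gap of 73.6 − 64.5 = 9.1 points.

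**Success.** The stop at the interim is stated as binding, so

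P(success) = P(X1 = 2)·P(X2 ≥ 2) + P(X1 = 3)·P(X2 ≥ 1) + P(X1 ≥ 4), with X1 ~ Bin(20, p) and X2 ~ Bin(15, p).

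- p = 20%: 0.1369 × 0.8329 + 0.2054 × 0.9648 + 0.5885 = 0.1140 + 0.1981 + 0.5885 = 0.901. The printed 90% is reproduced.
- p = 5%: 0.1887 × 0.1710 + 0.0596 × 0.5367 + 0.0159 = 0.0323 + 0.0320 + 0.0159 = 0.080. The printed value is 0.09.

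Section 13.1.3 describes the design as one-stage with an interim analysis, so I also computed the single look at 35 patients. P(X ≥ 4 of 35) is 0.096 at 5% and 0.939 at 20%. That does not give 0.09 either, and it loses the match with the printed power.

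**Could a different design explain the printed figures?**
- *Another interim size.* With the stop at 1 or fewer and p = 5%, 24 patients give 66.1% and 25 give 64.2%. At p = 20% those sizes give 3.3% and 2.7%, not 7%. No interim size gives both 64.5% and 7%.
- *Another total.* With 20 at the interim and 37 in all, the success probability at 5% is 0.0898. The early-stopping probability does not depend on the total and stays at 73.6%.
- *Another null rate.* With 20 patients, 64.5% holds at a true rate of 6.2%, but the success probability there is 0.144. A success probability of 0.09 holds at 5.2%, where early stopping is 72.0%. No single rate gives both printed values.

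**The source of the 5%.** The text of 13.1.1, set side by side:

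| Statement in 13.1.1 | Rate |
|---|---|
| Pazopanib study (reference 39) | 6.1% |
| Cetuximab-carboplatin study (reference 40) | 11.7% |
| Summary range | 6% to 20% |
| Rate credited to references 39 and 40 | around 5% |

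The only other 5% in the section is an ovarian cancer response rate cited to a different reference, so it is not the source.

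**Sensitivity of the rule.** At p = 6.1%: 0.2277 × 0.2319 + 0.0888 × 0.6110 + 0.0306 = 0.0528 + 0.0542 + 0.0306 = 0.138. At p = 11.7% the same formula gives 0.535; this is context only.

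**The case against.** The strongest reply concerns the 5%. The text says around 5%, and 6.1% is only 1.1 points away. The 6% at the bottom of the range looks like that same 6.1% rounded, and the 20% at the top matches the second-line cytotoxic rate that the section itself warns against. The more heavily pretreated cohort had the lower rate, and the endpoint here is confirmed response, so a round 5% can be read as a reasonable choice. This stands as a defence of choosing 5%. It does not defend naming both studies as its source when one is reported at more than twice that rate.

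For the same reason, a reader might infer that the null should be 6.1%, or that the trial's real false-positive rate is 0.138. The documents do not support either reading. They give no denominator for the 6.1% and do not say whether it counts confirmed responses. Treating the pazopanib study as the closer benchmark is a judgement: 13.1.1 calls both cohorts similar to this one, and eligibility criterion 3.1.5 admits patients after one line of chemotherapy. Section 13.1.5 makes no claim at 6.1%. Nor can 0.138 be called an upper bound, because 13.1.2 lets delayed responders after initial progression count in the final analysis, and the calculation does not model them. The 11.7% comes from a carboplatin combination given mostly after one prior line, so 0.535 is not an operating characteristic of this trial.

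On 13.1.5, one can say that the printed 0.09 is conservative against 0.080. That is true, and so is the printed 64.5% against 73.6%. It limits the harm but does not make the figures right.

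**Conclusion.** Both faults hold. The arithmetic one carries the point: at a true rate of 5% the early-stopping probability is 73.6%, where 64.5% is printed, and the success probability is 0.080, where 0.09 is printed. The 20% figures are right, which indicates that the rule is as intended and that the 5% figures are the ones in error. A reader might take the 6.2% root as a sign that the design was built on a different null. The documents do not support that, since 0.09 does not hold at 6.2%.

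The attribution fault is one of sourcing. It does not show that 5% is the wrong null.

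The calculations assume exactly 20 and 35 evaluable patients, a binding interim stop, independent patients with a common response rate, and no delayed responders. The errors do not weaken the rule, and no decision in the trial changes, so this should be corrected but does not call the design into question.

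**What to change.** In 13.1.5, replace the printed probabilities with the exact ones, for example: *Under the stated rule the exact probability of a positive result is 0.08 at a true confirmed response rate of 5% and 0.90 at 20%; the exact probability of stopping at the interim is 73.6% and 7%, respectively.*

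In 13.1.1, replace the sentence that credits 5% to references 39 and 40 with the two reported rates and their settings: 6.1% with pazopanib (median of 3 lines) and 11.7% with cetuximab-carboplatin (70% with one prior line). The sponsor should then give its own reason for using 5%. If that reason is an adjustment for confirmation, it should say so.

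Optionally, the sponsor may add as a sensitivity value that the rule's success probability is 0.14 at a true rate of 6.1%, noting that the documents do not say whether the 6.1% counts confirmed responses and that delayed responders are not modelled.

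The null, sample size, cut-offs and power are unchanged. The cost is a few sentences and a written reason for the 5%.
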